18.1.1.10 Total and organ specific numeric scores

Attribution of numeric values to each grade (derived above) is as follow:

Table 32: BILAG scoring

Grade	Numeric value
A	12
B	8
C	1
D	0
E	0

The total score is calculated as the sum of the organ domain scores.

If at least one organ domain score is missing, then the Total score is missing.

18.1.2 Physician Global Assessment

The PGA is used to quantify disease activity and is measured using an anchored VAS (see [Figure 1](#)). The PGA will be determined on a continuous VAS that asks the Investigator to assess the subject's current disease activity from a score of 0 (none) to 3 (severe), with the assessment made relative not to the subject's most severe state but the most severe state of SLE per the Investigator's assessment. As per its validation method, the PGA is recommended to be completed prior to laboratory results from the individual study visit being available ([Petri 1992](#)).

This version of the PGA is not scored blindly. The assessor is instructed to look at the previous month's PGA, decide whether the overall condition of the subject is same, better or worse and move the line accordingly.

A score change, where score is moved to the right from 2.5 or below in the previous month to > 2.5 this month, denotes an arbitrary threshold for severe flare to be considered when determining if enough change has occurred to justify assessing the criterion as severe flare. A score change ≥ 1 unit to the right denotes a designation of mild/moderate flare.

Figure 1: Physician Global Assessment Visual Analog Scale with Anchors

If a subject completely missed a visit, the PGA score from previous analysis visit will be used.

18.1.3 SLEDAI-2K

The Total score of the SLEDAI-2K is calculated as the sum of the weights of the descriptors marked as present by the investigator. The weights corresponding to each of the 24 descriptors are described in the table below:

Table 33: SLEDAI scoring

Descriptor	Weight
Seizure	8
Psychosis	8
Organic brain syndrome	8
Visual disturbance	8
Cranial nerve disorder	8
Lupus headache	8
Cerebrovascular accident	8
Vasculitis	8
Arthritis	4
Myositis	4
Urinary casts [#]	4
Hematuria [#]	4
Proteinuria [#]	4
Pyuria [#]	4
Rash	2
Alopecia	2
Mucosal ulcers	2
Pleurisy	2
Pericarditis	2
Low complement* [#]	2
Increased DNA binding* [#]	2
Fever	1
Thrombocytopenia [#]	1
Leukopenia [#]	1

*blinded descriptor

[#]laboratory components

Handling with blinded descriptor: As “Increased DNA binding” and “Low complement” are blinded items, the SLEDAI-2K total score will have to be derived for primary analysis with the laboratory unblinded values. “Increased DNA binding” item is defined as “>25% binding by Farr assay or above normal range for testing laboratory”. The parameter to take into account in laboratory data is “anti-Double Stranded DNA”. Increased DNA binding will be derived as ‘present’ if the anti-dsDNA value is positive (i.e. > 15 U/mL). “Low complement” item is defined as “decrease in C3 or C4 below the lower limit of normal for testing laboratory”. The parameters to take into account in laboratory data are “Complement C3” and “Complement C4”.

Total score used for statistical analysis will be re-calculated for all timepoints except screening and Day 1 with the unblinded values of Increased DNA binding and Low complement. The total score for the next visits as stated by the investigator in the eCRF will not be used in any statistical analysis.

Handling of missing items in SLEDAI-2K scores and change from baseline scores:

Actual scores

If the missing clinical component has weight > 4 in the overall score (see [Table 33](#)), then no imputation is performed. The SLEDAI-2K score will be missing.

If the missing clinical component has weight ≤ 4 in the overall score (see [Table 33](#)) or laboratory components missing, then the missing values will be imputed with the value of previous analysis visit. Only value assessed post-Day 1 dose (i.e. after baseline) can be used for imputation. If at least one item is still missing, then SLEDAI-2K score will be calculated based on available data.

If a subject completely missed a visit, the SLEDAI-2K total score from previous analysis visit will be used.

Change from baseline and SRI response

In general, SLEDAI clinical components are not expected to be missing.

In unlikely case of missing clinical value, change from baseline and thus SRI response (see [Section 14.1.1](#)) will be derived as follows:

- If the missing clinical component has weight > 4 in the overall score (see [Table 33](#)), then no imputation is performed. The SLEDAI-2K score will be missing and thus subject will be considered as non-SRI responder.
- If the missing clinical component has weight ≤ 4 in the overall score (see [Table 33](#)) or laboratory components missing, then the first step of imputation will be to carry forward the value of previous analysis visit (only value assessed while subject is on-treatment can be used for imputation). If that corresponding previous analysis visit value is also missing, then the component value will remain missing and the steps below will be followed:
 - Baseline SLEDAI-2K score will be re-derived with corresponding missing values at scheduled visit set to missing at Baseline visit
 - Change from baseline to analysis visit will be calculated and use as follows for SRI response derivation:
 - If there is a change from baseline ≥ 4 points reduction based on available non-missing components, then criterion #1 for SRI response is met
 - If there is an increase (i.e. worsening) or no change, or 1 to 3 points reduction based on available non-missing component, then the subject will be considered as non-SRI responder for that analysis visit

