Number and percentage of subjects taking immunosuppressants (excluding anti-malarials) (Baseline)	
 • Yes • No
Number and percentage of subjects taking anti-malarials (Baseline)	
 • Yes • No
Number of subjects with urine protein to creatinine ratio (UPCR) (Baseline)	
 • <0.5 mg/mg, • ≥0.5-1 mg/mg, • ≥1-1.5 mg/mg, • ≥1.5-2 mg/mg, • ≥2-3 mg/mg,

	
 • ≥ 3-4 mg/mg, • ≥ 4 mg/mg, • Missing.
Number of subjects with negative, indeterminate, positive or missing anti-dsDNA antibodies (Screening)	
 • Negative defined as < 10.0 U/mL, • Indeterminate as ≥ 10.0 and ≤ 15.0 U/mL • Positive defined by value > 15 U/mL • Missing
Antinuclear antibodies (Screening)	
 • Negative ($< 1:80$), • Positive ($\geq 1:80$), • Missing
Antinuclear antibodies and/or anti-dsDNA antibodies (Screening)	
 • Negative antinuclear antibodies and negative anti-dsDNA antibodies, • Positive antinuclear antibodies or positive anti-dsDNA antibodies (at least one test result is needed), • Missing antinuclear antibodies and missing anti-dsDNA antibodies.
Anti-Smith (Screening)*	
 • Negative (< 1.0 AI), • Positive (≥ 1.0 AI), • Missing
anticardiolipin IgG (Baseline)	
 • Negative (≤ 14 G phospholipids [GPL] U/mL), • Intermediate (15-20 GPL U/mL), • Low to medium positive (21-80 GPL U/mL), • High positive (> 80 GPL U/mL) • Missing
anticardiolipin IgM (Baseline)	
 • Negative (≤ 12 M phospholipids [MPL] U/mL), • Intermediate (13-20 MPL U/mL), • Low to medium positive (21-80 MPL U/mL), • High positive (> 80 MPL U/mL), • Missing
Antinuclear antibody associated with autoimmune diseases including Sjögren syndrome and systemic lupus erythematosus (anti-Ro/SSA antibody) (Baseline)	
 • Negative (< 1.0 AI), • Positive (≥ 1.0 AI), • Missing
Antinuclear antibody associated with autoimmune diseases including Sjögren syndrome (anti-La/SSB antibody) (Baseline)	
 • Negative (< 1.0 AI), • Positive (≥ 1.0 AI), • Missing

Low C3 complement (Screening)	
 • Low (< LLN) • Normal (within normal ranges [NRs]) • High (>ULN) • Missing (NRs for C3: 90-180 mg/dL)

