14.1.1 Definitions

The two-primary efficacy endpoints are SRI response at Week 52:

- SRI-4 response in all subjects,
- SRI-6 response in the HDA subgroup.

The SRI-4 response, a measure of reduced SLE disease activity, is defined by meeting all of the following conditions compared to Baseline:

1. ≥ 4 -point reduction in SLEDAI-2K total score.
2. No significant worsening in PGA score (< 0.3 increase assuming the PGA score is on a 0-3 scale).
3. No new BILAG A organ domain scores and ≤ 1 new BILAG B organ domain score compared to Day 1 using BILAG 2004.
4. No institution of EAC-determined protocol-prohibited medication/treatment (i.e., EAC-treatment failure)

Subjects with missing values at Week 52 after the implementation of rules defined in Appendices 18.1.1 and 18.1.3 will be considered as non-responder in the primary analysis.

Assessment of criterion #4 will be confirmed by an Endpoint Adjudication Committee (EAC). Further details can be found in the EAC Charter.

The SRI-6 response is defined similarly to SRI-4, based on a ≥ 6 -point reduction in SLEDAI-2K total score.

Details of derivation are described in Appendix 18.1.

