18.1.7 LLDAS

LLDAS status is defined as meeting all the following (Franklyn 2016):

- SLEDAI-2K ≤ 4 and no activity in any major organ systems (renal, central nervous system, cardiopulmonary, vasculitis, fever):
 - Derived from CRF form ‘SLEDAI1’, ‘SLEDAI2’, ‘SLEDAI3’ depending on the visit. In order to meet this criterion, the descriptors “seizure”, “psychosis”, “organic brain syndrome”, “visual disturbance”, “cranial nerve disorder”, “lupus headache”, “CVA”, “vasculitis”, “Urinary casts”, “hematuria”, “proteinuria”, “pyuria”, “pleurisy”, “pericarditis” & “fever” must be absent (score=0) with the exception of the following descriptors: “arthritis”, “myositis”, “rash”, “alopecia”, “mucosal ulcers”, “low complement”, “increase DNA binding”, “thrombocytopenia”, “leukopenia”. The above items can be present, however, the total score of them (if present) cannot be larger than 4, assuming all zeros being observed (i.e., absence) for the other descriptors.
- PGA ≤ 1 (scale 0-3)
- No new features of disease activity compared with the assessment of previous analysis visit
 - this criterion is derived from the SLEDAI-2K questionnaire: no new features (absent) compared with previous visit (absent = score 0 / present = score > 0) for each item
- Prednisone-equivalent ≤ 7.5 mg/day at each visit (see Table 49 and Table 50)
- No institution of EAC-determined protocol-prohibited medication/treatment (i.e., EAC-treatment failure)
 - This must be a case-by-case review and defined via Medical Review, and then confirmed by the EAC.

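### The two serology items of SLEDAI-2K are investigator-marked at baseline but laboratory-derived later, so the change behind SRI-4 and SRI-6 may include 2 artefactual points, 4 at worst

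*SAP*

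**What the plan says.** Section 14.1.1 makes the SRI a change measure: it "is defined by meeting all of the following conditions compared to Baseline", the first condition being a fall of at least 4 points in the SLEDAI-2K total (6 for SRI-6).

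Section 18.1.3 describes the total in four ways:

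- In general it is "calculated as the sum of the weights of the descriptors marked as present by the investigator". Increased DNA binding and Low complement weigh 2 points each (Table 33) and are flagged as blinded descriptors.
- Because of the blinding, "the SLEDAI-2K total score will have to be derived for primary analysis with the laboratory unblinded values". No timepoint is excepted here. The programmed rule is anti-dsDNA above 15 U/mL, and C3 or C4 below the lower limit of normal.
- The next paragraph makes an exception: "Total score used for statistical analysis will be re-calculated for all timepoints except screening and Day 1 with the unblinded values" of those two items.
- Finally, "The total score for the next visits as stated by the investigator in the eCRF will not be used in any statistical analysis". Only the visits after Day 1 are barred, so the Screening and Day 1 totals remain the investigator's. Table 4 agrees for Screening, taking the HDA score from the SLEDAI1 eCRF form.

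Section 18.1.7 takes the SLEDAI-2K criteria of LLDAS from the eCRF: "Derived from CRF form" SLEDAI1, SLEDAI2 or SLEDAI3, depending on the visit. It counts both serology items within the limit of 4.

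**The concern.** A change score is interpretable only if both ends are measured the same way. Here two items worth 4 points together come from an investigator's mark at baseline and from a laboratory algorithm at Week 52. The threshold for SRI-4 is itself 4 points. Any disagreement between the routes enters the change directly, in either direction, for both primary endpoints and for the key secondary SRI-4 in serologically active subjects.

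The text also leaves the programmer with two instructions: a general rule to use laboratory values, and an exception for Screening and Day 1. Section 18.1.4 adds to the doubt, because it re-calculates the SFI from the laboratory-based total without saying which Day 1 total feeds the first comparison. The SAP plans no concordance check and no sensitivity analysis on the point.

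**Working it through.** **1. Source of the serology points, by visit**

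| Visit | Source | Rule stated |
|---|---|---|
| Screening, Day 1 | Investigator's eCRF mark | Laboratory results and cut-off used are not stated |
| After Day 1 | Laboratory values, programmed | anti-dsDNA > 15 U/mL; C3 or C4 < LLN |

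**2. Possible artefact per subject.** With true serology unchanged and each item coded 0 or 1:

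spurious change = 2 × (lab DNA + lab complement) − 2 × (eCRF DNA + eCRF complement)

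Over all combinations this takes the values −4, −2, 0, +2 and +4. Negative values look like improvement.

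- *Anti-dsDNA.* Section 18.1.3 gives the instrument's wording, more than "25% binding by Farr assay or above normal range for testing laboratory", and then the 15 U/mL rule. Table 12 has a middle band: "Indeterminate as ≥ 10.0 and ≤ 15.0 U/mL". A steady 12 U/mL marked present on Day 1 scores 2 there and 0 later, a spurious fall of 2. A real 2-point fall would then meet the SRI-4 threshold. In the other direction, a +2 artefact turns a real 4-point fall into 2.
- *Complement.* There is one definition only, C3 or C4 below LLN. Reaching 4 points needs a discordant complement mark as well, through another sample, another laboratory or a scoring error.

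**3. The plan's own power figure (section 8.2.1).** Inputs: 103 per group, one-sided 0.0125 per endpoint, half of subjects HDA (about 51.5 per group).

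- SRI-4, 40% vs 60%: power 74.0%.
- SRI-6 in HDA, 30% vs 55%: 63.1%; at 30% vs 50%: 43.1%.
- At least one success depends on the correlation of the two tests, which the SAP does not give. At 0, 0.5, 0.7 and 0.9 it is 90.4%, 83.8%, 80.5% and 76.3%. With the weaker SRI-6 effect it is 85.2%, 78.9%, 76.3% and 74.2%.

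The stated 80% and 76% are reproduced at a correlation of about 0.7.

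**4. Effect of misclassification on SRI-4.** The flip rates are assumptions, equal across arms. With false-positive rate fp and false-negative rate fn:

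observed difference = (60 − 40) × (1 − fp − fn)

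| fp = fn | Difference |
|---|---|
| 2% | 20 × 0.96 = 19.2 points |
| 3% | 20 × 0.94 = 18.8 points |
| 5% | 20 × 0.90 = 18.0 points |

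If flips go one way only, from non-responder to responder:

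| fp | Rates | Power for SRI-4 alone |
|---|---|---|
| 0 | 40.0% vs 60.0% | 74.0% |
| 2% | 41.2% vs 60.8% | 72.0% |
| 5% | 43.0% vs 62.0% | 69.1% |
| 10% | 46.0% vs 64.0% | 64.1% |

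Flips of the same size from responder to non-responder give the same power.

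**5. Other endpoints**

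- *SFI (18.1.4).* A Day 1 eCRF total of 11 with one serology item unmarked becomes 13 at the first laboratory-scored visit. That rise to above 12 is a severe flare by definition.
- *BICLA (18.1.8).* One criterion is no worsening of the SLEDAI-2K total from Baseline; a +2 artefact fails it.
- *LLDAS (18.1.7).* Arthritis (4) plus low complement (2) is 6 by the laboratory rule. It is 4, within the limit, if the blinded item is absent from the CRF form.

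**The case against.** A reader might infer that investigators used a different anti-dsDNA cut-off at baseline, or that 4 points of the primary endpoint are artefact. The SAP supports neither. The Farr and normal-range wording is the instrument's item definition, which the next sentences translate into the trial's rule; it is not a documented investigator cut-off. Marking 12 U/mL as present also means treating a result that Table 12 calls indeterminate as positive. For complement no second cut-off exists.

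The exception has a benign reading. Totals are re-calculated because the items are blinded. Exempting Screening and Day 1 suggests serology was not yet blinded then, so the eCRF marks may already reflect study-laboratory results. Central values existed at Screening (Table 4). How sites scored Day 1 may be set out in the protocol or a manual that is not at hand.

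On consequences, a 2-point error changes SRI status only for subjects near the threshold. A 3-point SLEDAI-2K rise is only a mild/moderate SFI flare, whereas the time-to-flare and rate endpoints use severe flares. For LLDAS, section 18.1.3 can be read as overriding the form names in 18.1.7.

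These points limit the size and the certainty. They do not remove the difference in route, the conflict between adjacent paragraphs of 18.1.3, or the lack of any planned check. On LLDAS, 18.1.7 still names the CRF forms as its source although two items are blinded, so the two sections conflict.

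Timing also counts. Sections 6.3 and 6.4 say the study was terminated after review of the primary results, so replacing the primary baseline in version 4.0 would be post hoc.

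**Conclusion.** The concern holds as a measurement inconsistency of moderate severity. The possible artefact is 2 points if only the anti-dsDNA mark is discordant, 4 points in the worst case, and zero if investigators applied the same laboratory results and rule.

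A reader might also infer bias towards the drug. The documents do not support that: the baseline marks belong to a randomised, double-blind comparison, so discordance should be balanced across arms. The expected result is attenuation. The reduction to 19.2–18.0 points and the fall in SRI-4 power rest on assumed flip rates applied equally to all arms. The SAP gives no discordance rate, so the true size is unknown. The LLDAS mismatch is a separate, smaller inconsistency.

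**What to change.** - **Section 18.1.3.** Re-derive the two serology items of the baseline total from the last available pre-dose central-laboratory anti-dsDNA, C3 and C4, using the later-visit rules. Use that baseline for change, SRI, BICLA and the first SFI comparison. Remove the conflict between the general rule and the exception.
- **Version 4.0.** As the primary results had been reviewed, report this as a sensitivity analysis, with a table of eCRF against laboratory marks at baseline for each item.
- **HDA stratum.** Keep the eCRF Screening score.
- **Section 18.1.7.** Derive the SLEDAI-2K criteria of LLDAS from the items re-calculated under 18.1.3 instead of the CRF forms.

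The cost is SAP wording, programming and one added analysis. Section 18.1.3 already re-derives the baseline score for components missing at a later visit, so the step is not new in kind. The legible text confirms central results at Screening but not on Day 1, hence the last-available rule. The downside is that the analysed baseline total will differ from the eCRF total for some subjects, and that HDA status and baseline will then rest on different sources.

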18.1.4 SLEDAI Flare Index

The SFI can be used with any version of the SLEDAI and will be used with the SLEDAI-2K for the purposes of this trial.

A mild/moderate flare is defined as any of the following

- Increase in SLEDAI-2K total score of 3 points or more (but total score not to more than 12).
- New or worse discoid, photosensitive, profundus, cutaneous vasculitis, bullous lupus; or nasopharyngeal ulcers; or pleuritic; or pericarditis; or arthritis; or fever due to SLE.
- Increase in prednisone, but not to > 0.5 mg/kg/day.
- Added NSAID or hydroxychloroquine (or chloroquine) for SLE activity.
- ≥ 1.0 increase in PGA score, but score not to exceed 2.5 (assuming the PGA score has been transformed to a 0-3-point scale).

A severe flare is defined as any of the following:

- Increase in SLEDAI-2K total score leading to total score > 12.
- New or worse central nervous system SLE; or vasculitis; or nephritis; or myositis; or platelets < 60,000/mm³, or hemolytic anemia with hemoglobin < 70 g/L or decrease in hemoglobin > 30 g/L AND requiring: double prednisone, or prednisone increase to > 0.5 mg/kg/day, or hospitalization due to SLE.
- Increase in prednisone to > 0.5 mg/kg/day.
- New cyclophosphamide, azathioprine, methotrexate, or mycophenolate for SLE activity.
- Hospitalization for SLE activity.
- Increase in PGA score leading to total score > 2.5 (assuming the PGA score has been transformed to a 0-3-point scale).

SFI used for statistical analysis will be re-calculated with the SLEDAI-2K total score derived with the unblinded value of Increased DNA binding and Low complement.

Subjects with missing SFI assessment for a visit will be counted as missing in the SFI summary statistic table for that visit.

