18.1.8 BICLA Response

Requirements for BILAG-based Composite Lupus Assessment (BICLA) response are (Clowse 2017), to be assessed in the subgroup of subjects with at least one A and/or two B at Baseline:

1. BILAG 2004 improvement (all A scores at Baseline improved to B/C/D, and all B scores improved to C or D);
2. No worsening in disease activity (no new BILAG 2004 A scores and ≤ 1 new B score) from Baseline;
3. No worsening of total SLEDAI-2K score from Baseline;
4. No significant deterioration ($< 10\%$ worsening) in visual analogue PGA from Baseline

5. No institution of EAC-determined protocol-prohibited medication/treatment (i.e., EAC-treatment failure).

Assessment of treatment failure will be confirmed by the EAC.

Handling of missing criteria

Missing values in BILAG organ domain scores and SLEDAI-2K total scores will be handled as detailed in appendices [18.1.1](#) and [18.1.3](#).

18.2 Revised American College of Rheumatology Classification Criteria for Systemic Lupus Erythematosus

For the purpose of identifying subjects in clinical studies, a person shall be said to have systemic lupus erythematosus if any four or more of the 11 criteria are present, serially or simultaneously, during any interval of observation (Hochberg 1997, Tan 1982).

Table 35: ACR Criteria for Classification of SLE

Criterion	Definition
1. Malar Rash	Fixed erythema, flat or raised, over the malar eminences, tending to spare the nasolabial folds
2. Discoid Rash	Erythematous raised patches with adherent keratotic scaling and follicular plugging; atrophic scarring occur in older lesions
3. Photosensitivity	Skin rash as a result of unusual reaction to sunlight, by patient history or physician observation
4. Oral Ulcers	Oral or nasopharyngeal ulceration, usually painless, observed by physician
5. Nonerosive Arthritis	Involving two or more peripheral joints, characterized by tenderness, swelling, or effusion
6. Pleuritis or Pericarditis	1. Pleuritis: convincing history of pleuritic pain or rubbing heard by a physician or evidence of pleural effusion or 2. Pericarditis: documented by electrocardiogram or rub or evidence of pericardial effusion
7. Renal Disorder	1. Persistent proteinuria: > 0.5 g per day or > than 3+ if quantitation not performed or 2. Cellular casts: may be red cell, hemoglobin, granular, tubular, or mixed

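### SLEDAI-2K items still missing after carry-forward are scored as absent, so a partial total can establish low disease activity and can upgrade a recorded SFI flare to severe

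*SAP*

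**What the plan says.** SAP 18.1.3 defines the score as follows: "The Total score of the SLEDAI-2K is calculated as the sum of the weights of the descriptors marked as present by the investigator". For actual scores, a missing clinical item of weight above 4 makes the score missing. For the others ("If the missing clinical component has weight ≤ 4 in the overall score", or any laboratory item) the previous analysis visit supplies the value, with one limit: "Only value assessed post-Day 1 dose (i.e. after baseline) can be used for imputation". For whatever is then still missing, the rule is: "If at least one item is still missing, then SLEDAI-2K score will be calculated based on available data".

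For change from baseline and SRI the same section adds a correction: "Baseline SLEDAI-2K score will be re-derived with corresponding missing values at scheduled visit set to missing at Baseline visit". No matching correction is stated where the actual score itself is used:

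- LDA (total of 2 or less, with a clinical version that drops anti-dsDNA and complement) and the 4-or-less part of LLDAS (14.3.1, 18.1.7). Table 19 gives these the data handling of Table 17, where a missing Week 52 response is a non-response.
- The SFI (18.1.4), which is recalculated from the derived total. One of its severe criteria is "Increase in SLEDAI-2K total score leading to total score > 12".

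BILAG is handled differently: 18.1.1.10 sets the total to missing when any organ domain score is missing.

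**The concern.** In a weighted sum without proration, leaving an item out gives the same number as scoring it absent. The SAP allows for this in SRI by stripping the item from baseline too. An absolute threshold has no baseline to strip, so the fewer items are measured, the easier it is to pass. This runs against the handling the SAP chose for LDA and LLDAS, which is meant to count missing data against the subject. Since a partial total exists, the status is not missing and the non-response rule has nothing to act on.

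In the SFI the error runs the other way: an item that returns looks like worsening. Severity is re-derived from the total, so the return can move a flare into the severe class that feeds time to first severe SFI flare and the severe SFI annualized rate.

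**Working it through.** The SAP states no figure for residual missing items, so there is none to reproduce. Inputs: item weights from Table 33, thresholds from 14.3.1, 18.1.4 and 18.1.7, and 469 randomized subjects from 8.2.2.

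**1. Reach of the rule.** All 24 items: 8×8 + 6×4 + 7×2 + 3×1 = 105 points. The eight items of weight 8 are exempt because they make the score missing. The rule reaches the other 16 items: 24 + 14 + 3 = 41 points. Eight of these are laboratory items: 4×4 + 2×2 + 2×1 = 22 points.

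**2. Absolute thresholds.** Items still missing after carry-forward:

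| Use | Truly present | Still missing | True | Scored | Result |
|---|---|---|---|---|---|
| LDA, ≤ 2 | low complement 2, DNA binding 2 | both | 4 | 0 | responder |
| LDA, ≤ 2 | rash 2, leukopenia 1 | leukopenia | 3 | 2 | responder |
| Clinical LDA, ≤ 2 | rash 2, pyuria 4 | pyuria | 6 | 2 | responder |
| LLDAS, ≤ 4 part | rash 2, low complement 2, DNA binding 2 | low complement | 6 | 4 | this part met |

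**3. SFI severity.** Arthritis 4 + rash 2 + alopecia 2 + mucosal ulcers 2 + low complement 2 + DNA binding 2 = 14. With both serology items missing and nothing to carry forward, the score is 14 − 4 = 10. At the next visit, with unchanged disease, it is 14: a rise to above 12. If a mild or moderate flare is recorded at that visit for another reason, it is re-derived as severe. On the items scored at both visits the comparison is 10 with 10, a change of 0.

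**4. Frequency, by assumption only.** Let an item be missing at a visit with probability q = 1 to 5%, and let carry-forward reach back one visit. The number with a residual missing item at Week 52 is 469 × q × P(missing at Week 48 given missing at Week 52).

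- Independent visits: 469×0.01×0.01 = 0.05, to 469×0.05×0.05 = 1.17.
- With 30% also missing at Week 48: 469×0.01×0.30 = 1.41, to 469×0.05×0.30 = 7.04.
- Week 4, if no earlier post-baseline value exists: 469×0.01 = 4.7, to 469×0.05 = 23.45.

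Only subjects in whom the item was truly present, and whose total lies near the threshold, are misclassified.

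**The case against.** A reader might infer more than the SAP supports. These limits stand:

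- **SRI.** It has the baseline correction, so the two-primary endpoints and the key secondary SRI-4 endpoint are not shown to be affected. The other key secondary endpoint rests on BILAG.
- **BICLA.** Criterion 3, "No worsening of total SLEDAI-2K score from Baseline", is a change from baseline, and 18.1.8 refers missing values to 18.1.3. The correction there may well apply already.
- **New SFI events.** Time to first severe SFI flare takes its date from the eCRF flare form (14.3.2.1), and the notes to Tables 20 and 22 count eCRF records. DNA binding and complement are blinded descriptors, so an investigator seeing stable disease has no flare to record. The firm effect is an upgrade in severity, not an added event. Section 18.1.4 also does not name the comparison visit.
- **Clinical items such as arthritis.** The SAP says: "In general, SLEDAI clinical components are not expected to be missing". Laboratory items are the realistic route; the SAP makes no such statement about them.
- **Week 4.** It does not follow that every laboratory item missing at Week 4 is scored absent. Tables 53 and 54 give urine and hematology data a Week 2 window. If carry-forward uses laboratory windows, a value may exist for six items worth 18 of the 22 laboratory points. The SLEDAI-2K windows in Table 51 start at Week 4.
- **LLDAS.** Renal items must separately be absent, although the SAP does not say how a missing one is read.
- **Week 52.** If carry-forward is chained visit by visit, a residual missing item requires that no post-baseline value exists at all. The SRI text, which leaves an item missing when the previous visit's value is missing too, favours the one-step reading. The actual-score text does not settle it.
- **High disease activity.** A larger effect in this subgroup might be inferred from the cut at 12, but no figure supports it.

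None of this removes the core defect: no rule in the SAP stops a partial total from establishing LDA.

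**Conclusion.** The concern holds in limited form. A laboratory item, or a clinical item of weight 4 or less, that is still missing after carry-forward is scored as absent. A subject can then be classed as LDA, or meet the 4-or-less part of LLDAS, where missing should mean non-response. Clinical LDA is exposed only through items other than serology. On the assumption that the SFI compares with the previous visit, a returning item can also upgrade a recorded flare to severe.

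The size is unknown and probably small at Week 52: under the assumptions above, at most about 7 of 469 subjects per item would have a residual missing value, and fewer would be misclassified. The endpoints are other secondary with nominal p-values (14.3), so this is a correction worth making and no threat to the trial's main conclusions.

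**What to change.** In 18.1.3, for endpoints with an absolute threshold, add the weights of the still-missing items to the available total. If the sum could exceed the threshold (2 for LDA, 4 for LLDAS), the status is missing and so non-response under Table 17. For example, 0 with leukopenia missing gives at most 1 and LDA stands; 2 with leukopenia missing gives at most 3 and it does not. If the available items alone exceed the threshold, the subject is a non-responder anyway.

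In 18.1.7, treat a missing major-organ item as not shown to be absent. In 18.1.4, name the comparison visit and judge the SLEDAI-2K increase only on items scored at both visits. State in 18.1.3 whether carry-forward is one step or chained, and whether Week 2 laboratory values may be used.

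The primary analysis results had been reviewed before this SAP version (6.3, 6.4). For the primary analysis, report the change as a labelled sensitivity analysis with a count of residual missing items by visit and arm; apply it directly to the remaining LTE derivations. Section 14.6 stops imputing efficacy assessments missing after the termination announcement. If that covers single items, one missing laboratory item there would be scored as absent with no carry-forward at all.

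The cost is a small derivation change on data already collected, and possibly slightly lower LDA and LLDAS rates. In the SFI comparison, a truly new item whose previous value is missing would no longer count towards the increase.
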